### **3.2.19 Study Completion Procedures**

When the required number of confirmed cases of HZ have accrued, or if the decision is made to terminate the study early following a recommendation made by the DMC based on safety concerns, futile efficacy results from the interim futility analyses, or successful efficacy results from the interim efficacy analysis (see Section 3.5.8.1), the study will begin to enter the close-out phase. If this occurs, the study will continue to allow all patients to complete a minimum of 1 year post-vaccination follow-up for safety and efficacy (including new cases of HZ in these patients). At that time, no additional suspected HZ cases will be accrued, and any patient currently entered into suspected HZ follow-up will complete their 6-month assessment period. All patients must complete at least 1 year of follow-up following the last vaccination prior to completing the study. At the end of the safety follow-up period, all patients will be contacted by telephone to complete the study close-out questionnaire. Data generated from these questions will include any previously unreported symptoms of suspected HZ and SAEs, as well as the patient's final study disposition (e.g., completed, lost to follow-up, death).

### **3.2.20 Discontinuation/Withdrawal from Study**

Subjects/patients may withdraw at any time or be dropped from the study at the discretion of the investigator should any untoward effects occur. In addition, a subject/patient may be withdrawn by the investigator or the SPONSOR if he/she violates the study plan or for administrative and/or other safety reasons. The investigator or study coordinator must notify the SPONSOR immediately when a subject/patient has been discontinued/withdrawn due to an adverse experience (telephone or FAX). When a subject/ patient discontinues/withdraws prior to study completion, all applicable activities scheduled for the final study visit should be performed at the time of discontinuation. Any adverse experiences which are present at the time of discontinuation/withdrawal should be followed in accordance with the safety requirements outlined in section 3.4 SAFETY MEASUREMENTS - DETAILS.

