### **2.3.2 Continuation in the Study under Special Circumstances**

A patient should not receive additional doses of vaccine or placebo but should remain in the study to be followed for safety, efficacy and immunogenicity if:

- The patient develops a severe allergic reaction to a component of the vaccine (i.e., swelling of the mouth and throat, difficulty breathing, hypotension or shock) following administration of the prior vaccine dose.
- The patient becomes pregnant.
- The patient undergoes hematopoietic cell transplant (HCT).

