## **2.4 STUDY DESIGN AND DURATION**

### **2.4.1 Summary of Study Design**

This is a randomized, double-blind (with in-house blinding procedures), placebo-controlled, multicenter study to evaluate the efficacy, immunogenicity, safety and tolerability of V212 in adults with STM or HM. The study will enroll patients who are 18 years of age and older who have either STM or HM and are receiving chemotherapy. **(Note: In India only, enrollment is restricted to patients 18 to 65 years of age.)** In addition, patients 50 years of age and older who have HM, not in remission, will be enrolled regardless of whether they are receiving chemotherapy. **(Note: In India only, patients 50 to 65 years of age who have HM, not in remission, will be enrolled regardless of whether they are receiving chemotherapy.)**

Approximately 5264 patients (~2632 in the vaccine group; ~2632 in the placebo group), 18 years of age or older will be randomized to receive either V212 or placebo given as a 4-dose regimen administered ~30 days apart. **(Note: In India only, enrollment is restricted to patients 18 to 65 years of age.)** Randomization will be stratified by baseline medical condition with approximately 2696 patients with STM (receiving chemotherapy) and 2568 patients with HM enrolled into the study. Patients with HM will be further stratified into one of two strata, low immunocompromise (IC) or moderate to high IC, based on the patient's HM diagnosis and/or chemotherapeutic regimen (see Appendix 6.1). The planned randomization schedule by vaccination group is shown in Section 2.4.2. Enrollment for this study is expected to be completed in approximately 36 months.

This is an event-driven study based upon the occurrence of confirmed HZ cases. The combined dropout rates and the combined HZ event rates will be monitored on an ongoing basis using the blinded database. Patients will remain in the study from the time of enrollment until accrual of the targeted number (~90) of confirmed HZ cases in the STM population.

The planned study duration stated in this protocol is estimated based upon assumptions related to enrollment rate and follow-up time and HZ incidence in these populations. If these assumptions are met, the study will continue for approximately 5 years in order to accrue approximately 90 confirmed HZ cases. However, it should be noted that:

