#### **3.2.20.1 Discontinuation/Withdrawal Criteria**

As indicated in Section 2.3.2, a patient who discontinues from the study due to pregnancy or allergic reaction to a component of the vaccine, or who unexpectedly undergoes HCT should not receive subsequent vaccinations but should remain in the study for safety, efficacy and immunogenicity follow-up.

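### Section 3.2.20 permits removal from the whole study without separating the end of vaccination from the end of follow-up, contrary to Section 2.3.2 and to the retention the MITT analysis relies on

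*Combined protocol and SAP*

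**What the plan says.** Section 3.2.20 gives two powers of removal. The investigator alone has the first: "Subjects/patients may withdraw at any time or be dropped from the study at the discretion of the investigator should any untoward effects occur". No severity threshold is attached, and the removal is from the study, not from dosing. The second is shared: "a subject/patient may be withdrawn by the investigator or the SPONSOR if he/she violates the study plan", and it extends to administrative and other safety reasons. When a patient leaves, "all applicable activities scheduled for the final study visit should be performed at the time of discontinuation", and adverse experiences present at that time are followed. No later HZ contact is described.

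Section 2.3.2 takes the other approach for severe allergic reaction, pregnancy and HCT: "A patient should not receive additional doses of vaccine or placebo but should remain in the study to be followed for safety, efficacy and immunogenicity". Section 3.2.20.1 repeats this for the same three situations, but describes the person concerned as "a patient who discontinues from the study due to pregnancy or allergic reaction to a component of the vaccine" and then, in the same sentence, requires that person to stay in the study.

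Section 2.4.1 states the intended retention: "Patients will remain in the study from the time of enrollment until accrual of the targeted number (~90) of confirmed HZ cases". Section 3.5.4.1 defines the MITT set as all randomized patients with at least one dose, analysed as randomized. Section 3.5.5.1.1 runs time at risk from enrollment and censors non-cases at the stop date of HZ surveillance.

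**The concern.** A patient who has an anaphylactic-type reaction must be kept under HZ and safety surveillance, while a patient with a milder reaction may be removed from it. That ordering has no statistical rationale, and it arises because one section treats stopping vaccination and leaving the study as the same act.

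An untoward effect occurs after randomization and may be related both to arm (placebo is the stabilizer without antigen) and to how ill the patient is. If it leads to removal, the remaining follow-up is censored for a reason that may be connected with HZ risk. The Cox model in Section 3.5.5.1.1 treats that censoring as uninformative, and the efficacy methods describe no sensitivity analysis for early withdrawal. Active collection of later SAEs also stops, in patients who have already had a safety event or a protocol problem. In an event-driven trial with a follow-up cap of about 5 years and no further STM enrollment (Section 3.1.2), each lost case is difficult to replace.

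**Working it through.** **1. The rules side by side.**

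| Situation | Section | Vaccination | Follow-up |
|---|---|---|---|
| Severe allergic reaction, pregnancy, HCT | 2.3.2 | stops | continues |
| The same three | 3.2.20.1 | stops | described as both discontinuing and remaining |
| Any other untoward effect | 3.2.20, investigator | not addressed separately | may end |
| Study-plan violation, administrative or other safety reason | 3.2.20, investigator or sponsor | not addressed separately | may end |

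No general rule covers a patient who stops dosing for a reason outside the three named. That HZ surveillance ends is an inference from removal from the study, immediate final-visit activities and the absence of any later contact; it is not stated in terms.

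**2. The plan's own power figure.** Under 1:1 allocation, treat the vaccine cases among 90 as binomial with p = HR/(1+HR).
- Null (VE 25%): p0 = 0.75/1.75 = 0.429. Alternative (VE 65%): p1 = 0.35/1.35 = 0.259.
- The largest count c with P(X ≤ c | p0) ≤ 0.0125 is 27 (actual level 0.0084).
- Power = P(X ≤ 27 | p1) = 0.842, which reproduces the 84.2% in Section 3.5.7.1.

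**3. What extra loss does to the case count.** Inputs from Section 3.5.7.1: 1348 per arm, placebo rate λ = 0.017 (taken as per person-year), vaccine rate 0.35 × 0.017 = 0.00595, and 3-year enrollment. The horizon is 5 calendar years from the first patient (Section 2.4.1). With uniform entry and exponential dropout at rate η, cases per arm are (1348/3) ∫₀³ λ/(λ+η) · [1 − exp(−(λ+η)(5−s))] ds, with η chosen to give the stated total dropout.

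| Total loss | Expected cases |
|---|---|
| 20% | 94.0 |
| 30% (plan) | 87.9 |
| 35% (assumed) | 84.8 |
| 40% (assumed) | 81.5 |

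The 30% row is within 3% of the plan's 90 (87.9/90 = 0.977). Exact power at VE 65% is 0.842 at 90 cases, 0.816 at 88, 0.806 at 85, 0.795 at 82 and 0.814 at 81. It moves unevenly because the critical count is a whole number. This step treats loss as unrelated to HZ.

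**4. Whether bias can be sized.** The documents give no discretionary-withdrawal rates, so any figure rests on assumptions. Suppose 20% of patients are frailer, with r times the HZ hazard, and all early removals (proportion d in an arm) come from them. Mean hazard among those retained is ((0.20 − d)r + 0.80)/(1 − d). The vaccine-to-placebo ratio of these means, f, multiplies the true HR.
- r = 2, d = 6% vaccine and 2% placebo: f = (1.08/0.94)/(1.16/0.98) = 0.971. A true VE of 25% appears as 1 − 0.75 × 0.971 = 27.2%.
- The same with the arms exchanged: f = 1.030, apparent VE 22.7%.
- r = 3, d = 10% and 4%: f = (1.10/0.90)/(1.28/0.96) = 0.917, apparent VE 31.3%. This removes half of all frailer vaccine recipients.

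Success depends on the lower confidence bound, not the point estimate. From step 2 it needs at most 27 of 90 cases in the vaccine arm, an estimated VE of about 1 − 27/63 = 57%. Using HR = 0.75f in the same binomial, the chance of false success is about 0.012 in the first scenario (0.0084 without bias; limit 0.0125) and about 0.023 in the third.

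**The case against.** Several points on the other side have force.

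- Section 3.2.20 is permissive: it directs no site to remove anyone. Elsewhere the plan expects incomplete dosers to stay, since Section 3.5.5.1.1 would summarize HZ in MITT patients given only 1, 2 or 3 doses. This stands as evidence of intent, but it makes the wording of Section 3.2.20 more out of place, not less.
- A reader might infer that a missed dose window leads to removal. Section 3.2.1 instead provides for consultation and a documented joint decision, so that example fails. Nor does the sponsor share the untoward-effects discretion.
- A reader might also infer that later SAEs and deaths are lost altogether. Section 3.2.20 follows adverse experiences already present. Section 3.4.5.1 requires SAEs and deaths to be reported through the study, and certain later events to be reported when the investigator learns of them. What stops is active, unselected collection.
- Investigators are blinded (Section 3.2.18), dropout is monitored on blinded data (Section 3.5.7.1), discontinuations due to adverse experiences are compared by arm (Section 3.5.5.3), and the DMC sees data by group. These can reveal differential removal but cannot recover the missing follow-up.
- The 30% loss is a total, so discretionary removals may already be inside it. This stands. The allowance protects the case count, however, not the validity of the comparison.
- With no further STM enrollment, many early post-dose removals may already have happened. The power to withdraw nevertheless continues through follow-up.

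**Conclusion.** The point holds as a conflict of wording with a real consequence for data collection. Sections 2.3.2, 3.2.20 and 3.2.20.1 cannot all be followed consistently, and Section 3.2.20 permits censoring that the MITT analysis and the retention statement in Section 2.4.1 do not foresee.

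The size of any bias cannot be derived from the documents, and neither can its direction. It would be tempting to read the 31.3% illustration as a null vaccine passing the 25% margin. The documents do not support that: the inputs are invented, the sign reverses with the arms, and a point estimate of 31.3% is far below the roughly 57% needed for success.

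The effect on case count is modest. Relative to the planned 30% loss, a total loss of 35% or 40% would cost about 3 or 6 expected cases (87.9 − 84.8 = 3.1; 87.9 − 81.5 = 6.4). Exact power would be near 80%, against 81.6% at 88 cases and the stated 84.2% at 90. This assumes exponential dropout, uniform entry and the plan's rates. The change is worth making because it is cheap and removes an avoidable source of missing primary-endpoint data.

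**What to change.** Reconcile Sections 2.3.2, 3.2.20 and 3.2.20.1 by defining two separate terms: discontinuation of study vaccination, and withdrawal from study follow-up. Correct the sentence in Section 3.2.20.1 so that it refers to the first. State that an MITT patient who stops vaccination for any reason continues the monthly HZ contacts and the three-monthly SAE contacts already in the Section 1.7 flow chart, with vital status established at the latter, unless the patient withdraws consent or is lost to follow-up. Record the reason for every withdrawal from follow-up.

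The change concerns data collection only. The rules on when vaccination stops are left as they are, and no clinical rule is proposed.

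The cost is amendment wording, IRB/ERC review where the revision counts as significant, communication to sites, and a few more telephone contacts, with the usual work-up of any suspected HZ they bring to light. Follow-up already lost cannot be recovered by the wording.

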#### **3.2.20.1 Discontinuation/Withdrawal Criteria**

As indicated in Section 2.3.2, a patient who discontinues from the study due to pregnancy or allergic reaction to a component of the vaccine, or who unexpectedly undergoes HCT should not receive subsequent vaccinations but should remain in the study for safety, efficacy and immunogenicity follow-up.

### **3.2.21 Committees**

#### **3.2.21.1 Clinical Adjudication Committee**

The CAC is composed of clinical evaluators who are experts in the fields of infectious diseases and oncology, who will adjudicate all suspected cases of HZ as well as any HZ-related complications. Members are external to the SPONSOR, and may include principal or secondary investigators of this study or other V212 studies. No SPONSOR employees are members of the CAC. CAC members are blinded to the study vaccination group assignment. Guidelines that detail the CAC process are described in separate documentation.

#### **3.2.21.2 Scientific Advisory Committee**

The Scientific Advisory Committee (SAC), composed of a Merck Clinical Monitor, Merck statistician, Merck Communications Department (MCD) representative and external scientific leaders in the therapeutic area/disease area, convenes to provide advice on the protocol design and statistical analysis plan and to interpret and publish the study results of the clinical trial. The SAC is an advisory collaborative group.

#### **3.2.21.3 Data Monitoring Committee**

An independent DMC will be established for continuous safety oversight during the study and to review data at each of the planned interim analyses. To fulfill its responsibilities, the DMC will review safety, tolerability, efficacy and demographic data according to vaccination group assignments periodically during the course of the study (prior to end-of-study unblinding).

The DMC will consist of individuals with pertinent expertise in the field. An unblinded SPONSOR statistician will perform analyses of the unblinded data to be provided to the DMC, but will not be a voting member of the committee. The DMC guidelines and details related to the unblinded statistical analysis of the data will be described in separate documentation.

The board will be responsible for periodically reviewing the available safety data to identify any critical safety issues in adverse experiences or other safety measures in order to make periodic recommendations to the SPONSOR, including recommending whether to terminate the study based on safety concerns. Interim efficacy analyses (details in Section 3.5.8) will also be provided to the DMC for review and recommendations regarding terminating the study early for futility or early success.

The DMC Chairman will be responsible for reporting post-meeting recommendations to a Steering Committee (SC) comprised of Merck Senior Management members who will hold the authority to discontinue the study in the event of overwhelmingly favorable or unfavorable efficacy results or safety concerns.

### **3.2.21.4 Steering Committee**

The Steering Committee (SC), composed of members of Merck Senior Management, will provide the overall scientific direction for the program and will receive and be responsible for deciding upon any recommendations made by the DMC to stop the study early.

## **3.3 EFFICACY/PHARMACOKINETIC/IMMUNOGENICITY, ETC. MEASUREMENTS**

### **3.3.1 HZ Case Determination**

#### **3.3.1.1 Clinical Adjudication**

All suspected cases of HZ will go through case adjudication by the CAC in a blinded fashion. The CAC is a committee of adjudicators with expertise in the diagnosis and management of HZ as well as the medical aspects of clinical trials. The CAC will determine if a suspected case is a confirmed case of HZ, in their clinical opinion, and if it is determined that this is a confirmed case; the CAC will make the final determination of the confirmed HZ complication(s) present. Upon case confirmation by the CAC, members will adjudicate the case relative to the composite HZ complication endpoint. For each case of suspected HZ, the study site must obtain all necessary information required for suspected cases of HZ (see Sections 2.5 and 3.2.17). Adjudication packages (AP) consisting of all documents related to the suspected case of HZ will be assembled and distributed to the CAC members for review. Specific details regarding AP contents, endpoint definitions, and adjudication procedures will be found in the V212 HZ Case Adjudication Committee SOP.

### 3.3.1.2 Final Case Determination

A final confirmed case of HZ is defined primarily on the PCR detection of VZV DNA in a skin lesion specimen. If the skin lesion PCR result is reported as VZV positive, HZ is confirmed. If the skin lesion PCR result is VZV negative, HZ is ruled out. If the skin lesion PCR sample is missing or the result is reported as inadequate, or if the clinical presentation of HZ did not include a rash, the final determination as to whether the suspected HZ case is confirmed is based upon the final CAC adjudication decision in accordance with the CAC SOP.

### 3.3.2 PCR Assay for Lesion Samples

Lesion samples should be obtained from all patients presenting with a rash associated with varicella or HZ or varicella-like/HZ-like rash at the first evaluation for suspected HZ. If both vesicles and pustules are present, vesicles are the preferred source for specimens. Samples should be collected using the kit supplied by the SPONSOR, and stored immediately at  $-20^{\circ}\text{C}$  until shipment. Detailed procedures on lesion sample collection/storage and shipping are provided in the Laboratory Manual.

The purpose of the VZV PCR assay is to detect VZV and herpes simplex virus (HSV) deoxyribonucleic acid (DNA) in specimens obtained from subjects suspected of having varicella or HZ. This is the primary assay used by the central laboratory. The assay is a real-time PCR assay that uses virus-specific primers and probes to detect and discriminate among wild-type/Oka-parent VZV (VZV-WT/VZV-P), Oka-type attenuated VZV (VZV-O), and HSV DNA (HSV types 1 and 2). Virus-specific amplification is multiplexed with  $\beta$ -globin-specific primers and VIC-labeled fluorescent probe to demonstrate the presence of amplifiable host cell DNA in the clinical specimen [46].

The PCR assay is based on TaqMan® sequence detection chemistry utilizing an oligonucleotide probe that is labeled at the 5' end with a fluorescent reporter dye and at the 3' end with a fluorescent quencher dye. This probe sequence lies between 2 amplification primer sequences on the target DNA. When the probe is intact, the proximity of the quencher dye greatly reduces the fluorescence emitted by the reporter dye. If the target sequence is present in the PCR reaction, then the probe anneals between the primer sites and is hydrolyzed by the 5' nuclease activity of TAQ DNA polymerase as this primer is extended. The hydrolysis of the probe separates the reporter dye from the quencher dye, thus increasing the reporter dye signal. As TAQ extends the primer, the probe is removed from the target strand so that the overall PCR process is not inhibited. With each PCR cycle, additional reporter dye molecules are cleaved from their respective probes, resulting in an increase in fluorescence intensity. Each reporter signal is normalized to an internal passive reference dye to adjust for fluorescence fluctuations and baseline corrected. After analysis of the raw fluorescent data by the instrument software, a fixed threshold value of 0.05 is assigned and a threshold cycle (Ct) is determined, which represents the PCR cycle at which reporter fluorescence increased above a baseline signal. The threshold cycle is inversely proportional to the starting concentration of DNA. Results for the assay are reported as the virus type for which the sample is positive: VZVWT, VZV-O, HSV or Negative.

### 3.3.3 PCR Assay for Whole Blood Samples

All patients presenting with varicella/varicella-like or an HZ/HZ-like rash or acute HZ symptom(s) will have two 10 mL whole blood samples collected in plastic Vacutainer tubes containing EDTA at the first evaluation for suspected HZ. The blood samples should be stored frozen at -20°C until they are shipped to the central laboratory. The DNA isolated from the blood sample will be analyzed by VZV PCR analysis as described in Section 3.3.2. Further details on collection, handling, storage and shipment will be provided in the Administrative or Laboratory Binder.

### 3.3.4 VZV Antibody gpELISA

Serum samples will be obtained from all patients in the STM study group Day 1 (prior to Dose 1) and at Visit 5 (~28 days Postdose 4) to measure VZV antibody concentrations by gpELISA. Five (5) mL of blood will be collected into a serum separator VACUTAINER tube WITHOUT GEL SEPARATOR. The blood should be allowed to clot in the collection tube for 30 to 60 minutes. Once clotted, the collection tube should not be allowed to sit at room temperature or refrigerated for more than 2 hours prior to centrifugation and separation of the serum from the clot. Do not refrigerate newly collected blood specimens; this will cause hemolysis. Serum should be frozen immediately into approximately 2 to 3 (2-mL) Starstedt tubes, using a sterile pipette, and stored at -20°C until shipment to the central laboratory. The freezer used to store the specimens must be a non-frost-free freezer.

The purpose of the gpELISA is to detect IgG antibody to VZV before and after vaccination with VZV-containing vaccine(s). This is the primary assay used to evaluate the serological response to the vaccine(s). This method detects antibodies to VZV glycoproteins (gp), which are purified by lectin affinity chromatography from MRC-5 cells infected with the KMcC strain of VZV. The reactivity of the sera to the gp antigens from uninfected MRC-5 cells (denoted as Tissue Culture Control [TCC] wells) is subtracted from the reactivity of the sera to the purified gp antigens. The assay and the purification of the VZV gp from VZV-infected cells are described [47-49]. Serum sample gpELISA titers correlate with neutralizing antibody titers [50].

For the gpELISA, VZV gp or TCC antigen is adsorbed to polystyrene microtiter wells and used as the solid phase antigen. Experimental, control, and standard curve sera are incubated in these wells (2 wells for each antigen). For each serum sample, a delta optical density (DOD) is calculated as the difference between the average optical density (OD) of the 2 VZV antigen wells and the average OD of the 2 TCC wells. Quantitation is obtained by comparison of sample DOD with a standard curve. Results for the assay are reported as concentration of antibody in gpELISA units/mL.

